5. Baseline Assessment: Baseline assessment will include participant characterization measures and intervention outcome measures. The session will last approximately one hour.
6. Randomization process: The randomization process is designed to achieve appropriate generation of the random allocation sequence and concealment of the allocation sequence. A researcher who is not involved in phone screening, video screening, or informed consent will generate the randomization list prior to the screening of the first person for the randomized, controlled trial. The randomization list will use computer-generated random numbers. The randomization list will be stratified with random permuted blocks. The stratification variable will be Mild Cognitive Impairment (MCI present versus absent). MCI will be defined by a MoCA score of 20-25. The block size will vary randomly between 4 and 6. Research personnel who perform phone screening, video screening, informed consent, or assessments will not be able to access the randomization list. After a potential participant has completed phone screening and video screening, has fulfilled all inclusion criteria, has demonstrated no exclusion criteria, has provided documented informed consent, and has completed baseline assessment, the researcher will unconceal the randomization assignment for the intervention: Group 1 (intervention first) versus Group 2 (intervention later). After assignment, the participant and the researcher who performed informed consent will not be blinded to group allocation.
7. Participants in Group 2 will be told they will begin the intervention 8 weeks later and in the meantime will be asked to complete assessments at 4 and 8 weeks after joining the study but before beginning the video chat participation. Participants in Group 1 will be given information about the general research expectations over the next 8 weeks and will be invited to sign up for a technology training session to learn how to use the OneClick system.

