10. Week-4 assessment: 4 weeks after being placed into Group 1 or Group 2, participants will be contacted to schedule a week-4 assessment. Participants in both groups will complete measures related to social connectedness, loneliness, isolation, and quality of life. Group 1 will additionally complete measures related to system usability and perceived enjoyment of the OneClick system. This assessment session will take approximately 1 hour will be administered by a blinded assessor remotely over video or phone. Participants will be informed at the beginning of the assessment not to reveal their group assignment. Both groups will receive \$25 for this session. For Group 1 only, an additional short, semi-structured interview will be administered over video or phone by an unblinded assessor. This will focus on ease of use, usefulness, enjoyment, satisfaction with the topics and conversation, suggestions for updates, and perceptions of social connectedness and will take 30-45 minutes. The interviews will be audiotaped and transcribed verbatim. Group 1 will receive \$15 for completing the interview.

11. After this week-4 assessment, a research team member will contact participants in Group 1 to address any questions and issues related to the intervention to help participants remain engaged in the next 4-weeks of intervention.
12. Week-8 assessment: 8 weeks after being placed into Group 1 or Group 2, participants will be contacted to schedule a week-8 assessment. Each group's assessment sessions and compensation will be identical to week-4 assessment. This ends Group 1 participation in the study. They will receive a study debriefing and thanked for their time.
13. After the week-8 assessment, a research team member will contact participants in Group 2 to schedule their technology training session (described in step #8).
14. Group 2 will now begin 8 weeks of video-chat intervention

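### At weeks 4 and 8 the blinded session includes OneClick measures for Group 1 only, so the battery itself can show the assessor each participant's arm

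*Protocol*

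**What the plan says.** Protocol section 7F, step 10, describes the week-4 assessment. Both groups complete the common outcome scales on connectedness, isolation, loneliness and quality of life. The next sentence reads "Group 1 will additionally complete measures related to system usability and perceived enjoyment of the OneClick system". The sentence after that reads "This assessment session will take approximately 1 hour will be administered by a blinded assessor remotely over video or phone". One safeguard follows: "Participants will be informed at the beginning of the assessment not to reveal their group assignment".

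A separate contact is then described for Group 1 alone: a "semi-structured interview will be administered over video or phone by an unblinded assessor". Of its content the protocol says "This will focus on ease of use, usefulness, enjoyment, satisfaction with the topics and conversation". The interview is the only part of the visit assigned to someone unblinded.

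Step 12 carries this to week 8, where each group's "assessment sessions and compensation will be identical to week-4 assessment".

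Step 6 adds a second safeguard, "Research personnel who perform phone screening, video screening, informed consent, or assessments will not be able to access the randomization list". It also says that, after assignment, "the participant and the researcher who performed informed consent will not be blinded to group allocation". Step 15 ends assessor masking only once Group 2 is in its own intervention period. The SAP's main comparisons are OneClick against waitlist at 4 weeks and at 8 weeks, each relative to baseline.

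**The concern.** The protocol plainly intends masked assessment at weeks 4 and 8, but the content of the session works against it. The two stated safeguards protect the randomization list and limit what participants say. Neither stops an assessor from inferring the arm from the questionnaires that are or are not on the list for that session.

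The two affected visits supply all the between-group data in the SAP. Participants are unblinded, so the assessor is the only remaining masked party. The sessions are conducted live, by video or phone, which leaves room for prompting, clarifying or encouraging differently by arm. A report that describes these outcomes as collected by a blinded assessor would also claim more than the written procedure secures.

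**Working it through.** The plan gives no figure to reproduce here. The check is a reading of the steps together, followed by a count of sessions.

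**Which measures fall inside the blinded session.** In step 10 the order is: common scales for both groups, OneClick measures for Group 1, then a sentence about this session and its blinded assessor. The natural reading is that the session includes both sets of measures. The interview is introduced afterwards as additional and has its own, unblinded assessor. The OneClick measures are therefore on the blinded side of the line.

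**What the assessor can infer.** There are two arms and the module goes to one. If it is present, the participant is in Group 1. If the session ends without it, the participant is in Group 2. Both arms are revealed, so sessions in both arms count.

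**Inputs for the count.** Planned enrolment is 106 + 70 = 176 (section 9A). The blinded visits are week 4 and week 8, so 2 (steps 10 and 12). Planned blinded sessions before dropout: 176 × 2 = 352.

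**Sessions whose outcome scores are taken after the battery can show the arm.** The available text does not give the order of measures, the mode of completion or whether the same assessor returns, so each case below is an assumption.

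| Assumed conduct | Week 4 | Week 8 | Total |
|---|---|---|---|
| Items last, battery not known beforehand, no assessor returns | 0/176 | 0/176 | 0/352 = 0% |
| Items last, battery not known beforehand, same assessor always returns | 0/176 | 176/176 | 176/352 = 50% |
| Items first, or the assessor must know beforehand which battery to run | 176/176 | 176/176 | 352/352 = 100% |

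Between the first two rows, if a fraction *r* of week-8 sessions is done by the assessor who saw that participant at week 4, exposure is 176*r*/352 = *r*/2. For example, *r* = 0.5 gives 88/352 = 25%.

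These are counts of sessions at risk of unmasking. They do not measure bias in the treatment effect or inflation of type I error; the documents give no basis for either.

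**The case against.** The strongest reply has four parts.

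- **Actual unmasking is not established.** The protocol says Group 1 will complete the extra measures. Self-completion, or giving them after the outcome scales, would fit that wording. Section 7B refers to attached research materials, which could fix order and mode. This stands as a limit: the finding concerns what the available text permits, and the 0% case is possible. But steps 10 and 12 are where the procedure is defined, and nothing there rules out the worse cases.
- **The added harm may be small.** Participants complete the scales themselves and know their arm, so reporting bias is present whatever the assessor knows. This also stands, and the fix does not touch it. It is no reason to leave an avoidable leak in a session labelled as blinded.
- **The fix closes only one route.** Participants may disclose their arm despite the instruction, and step 6 leaves the consenting researcher unblinded without expressly barring that person from assessing. This is correct. Moving the items cannot by itself guarantee masking.
- **Moving the measures could alter usability data.** User acceptance is among the aims in section 6A, and Group 2 gives its usability measures within an assessment session (steps 15 and 17). A change partway through could shift the setting for some participants. The effect on comparability should be slight, since Group 2's measures are themselves taken by assessors who are no longer blinded, but the date of any change should be recorded.

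**Conclusion.** The concern holds. As written, steps 10 and 12 put arm-specific measures inside the session meant to be masked, at both time points the SAP compares. Depending on conduct that the available text does not specify, between 0 and 352 of the 352 planned sessions (0% to 100%) have outcome scores exposed; items last with a returning assessor gives 176 (50%). The count assumes full enrolment of 176, no dropout, and that both presence and absence of the module are informative.

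Confidence is high that the asymmetry is in the text. How often masking is lost in practice, and what that does to the estimates, cannot be determined from the documents. This should be fixed because the conflict is with the protocol's own stated safeguards and the remedy costs little.

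**What to change.** In steps 10 and 12, take the OneClick usability and enjoyment measures out of the blinded session. Give them in the unblinded Group 1 interview, or as a self-completed form sent once the blinded session is over. State that the blinded session uses the same measures in the same order in both groups. The same amendment could say that the researcher who took consent does not assess that participant.

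If the measures must stay where they are, a lighter alternative is to state three things: they come after the outcome scales, the assessor does not know which battery applies until those scales are finished, and a different assessor conducts week 8. That corresponds to the 0% row above.

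If sessions have already run as written, document the order used and how often assessors repeated, record the date of any change, and qualify any claim of blinded assessment in the report.

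The cost is a wording amendment with its IRB review, and an interview a few minutes longer (my assumption) with the blinded session shorter to match. The interview is already scheduled at 4 and 8 weeks, already paid at $15, and already covers ease of use, usefulness and enjoyment. Ratings of enjoyment and ease of use are also collected after each event (step 9). Sample size, visits and outcomes do not change.

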## Section 8. PERFORMANCE SITES TO INCLUDE INTERNATIONAL, SCHOOL, AND COLLABORATIVE STUDIES

**8A. List all research sites for the protocol. For non-University of Illinois at Urbana-Champaign sites, describe their status of approval and provide contact information for the site. If the site has an IRB, note whether the IRB has approved the research or plans to defer review to the University of Illinois at Urbana-Champaign.**

### Performances Sites

#1 Participant's home

#2 UIUC

#3 CJE SeniorLife

If there are additional performance sites, include them on an attachment and check here:

**8B. Is this a multi-center study in which the Illinois investigator is the lead investigator, or the University of Illinois at Urbana-Champaign is the lead site?  Yes  No**

If yes, answer 8C and 8D. If no, proceed to Section 8E.

**8C. Who is the prime recipient of funding, if funded? University of Illinois at Urbana-Champaign**

**8D. What is the management and communication plan for information that might be relevant to the protection of research subjects (e.g. unanticipated problems involving risks to subjects, interim results, and protocol modifications)?** This is a multi-site, minimal risk clinical trial and as such will be monitored by an independent Safety Officer. The Principal Investigator (PI) [name] with support from [name] will be responsible for ensuring participants' safety on a daily basis. A Safety Officer (SO) has been appointed to provide data and safety monitoring oversight to monitor participant safety, evaluate the progress of the study, and review procedures for maintaining the confidentiality of data, quality of data collection, management, and analyses. [name], Associate Chair for Research, Department of Medicine, University of Illinois College of Medicine at Peoria will serve as the SO. [name] has extensive RCT experience. He is an internist with additional training in clinical trial methodology. He has 25 years of experience as a clinical trial investigator, including roles as Principal Investigator of federally-funded research grant protocols. [name] has served as a member of the Data Safety and Monitoring Boards for various clinical trials.

No adverse events are expected given that this is a behavioral intervention study of low risk involving use of computer/tablet to engage in conversations with other people over a video chat platform called OneClick. Nevertheless, we do have a protocol in place for documenting and reporting any events to the safety officer (SO).

Formal responses to alerts and adverse events will be followed by research staff immediately upon learning about such an event. When an adverse event is identified by a member of the research team, the event will be reported to the PI within 24 hours and recorded on the Adverse Event Form. The University of Illinois will be responsible for maintaining the events forms and submitting reports or summaries to the SO.

**8E. If subjects will be recruited from Illinois public or private elementary or secondary schools, additional deadlines and procedures may apply. Criminal background clearances might be required. Special consideration must be given to the exclusion of protected populations. Please contact the School University Research Relations ([[contact]](mailto:[contact])) for more information. Select one:  Illinois schools will be used  Illinois schools will not be used**

## Section 9. SUBJECT ENROLLMENT GOAL & EQUITABLE SELECTION OF SUBJECTS

**9A. For each performance site, indicate the estimated total number of participants.**

Performance Site	# Male	# Female	Total
#1 UIUC	53	53	106
#2 CJE Senior Life	35	35	70

#3			
TOTALS	88	88	176
If additional performance sites are included on an attachment, check here: 			
9B. Select all participant populations that will be recruited.			
Age:			
 Adults (18+ years old)  Minors ( $\leq$ 17 years old)  Specific age range, please specify : 65 and older			
Gender:			
 No targeted gender (both men and women will be recruited/included)  Targeted gender, please indicate :  Men/boys  Women/girls  Other, please specify :			
Race/Ethnicity:			
 No targeted race or ethnicity (all races and ethnicities will be recruited/included)  Targeted race or ethnicity, please specify :			
College Students:			
 No targeted college population  UIUC general student body  Targeted UIUC student population, provide the instructor or course information, name of the departmental subject pool, or other specific characteristics :  Students at institution(s) other than UIUC, please specify :			
Any research with students on UIUC's campus needs to be registered with the Office of the Dean of Students .			
Other:			
 Inpatients  Outpatients  People who are illiterate or educationally disadvantaged  People who are low-income or economically disadvantaged  People with mental or cognitive disabilities or otherwise impaired decision-making capacities  Adults with legal guardians  People who are non-English speaking  People with physical disabilities  Pregnant or lactating women, human fetuses, and/or neonates  Prisoners or people with otherwise limited civil freedoms  Other, please specify :			
9C. Describe additional safeguards included in the protocol to protect the rights and welfare of the populations selected above.			
We will include older adults with Mild Cognitive Impairment (MCI). They will be capable of providing Informed Consent. We will mitigate the risks of the fatigue and frustration during assessments by using highly trained personnel (e.g., graduate student with a minimum two years of experience working with older adults or a trained clinician, such as a speech-language pathologist). At UIUC, personnel will be			

supervised by [name] who is a clinician by training and has over two decades of experience conducting research involving older adults with cognitive impairment. At CJE, personnel will be supervised by [name] who is also a clinician by training with extensive experience conducting research involving older adults with cognitive impairment. We will make sure to provide encouragement, scheduled breaks, and a supportive environment for the participant. Care will be taken to minimize any feelings of anxiety or discomfort aroused in the participant. Before participants begin assessments, they will be informed that there are no right or wrong answers for the structured interviews or questionnaires. Participants will be informed that if they experience anxiety or discomfort at any point to let us know and we can stop testing immediately. It is important to note that the measures proposed for the study are extensively used for participant testing in the context of studies on aging.

The intervention involves general conversations using the OneClick platform about topics of interest that promote positive reminiscing. We will offer 60 unique events (5/week) that cover a range of topics (e.g., pets; family traditions; baking) that promote reminiscing during conversation, known to produce positive affect in older adults. Participants will be encouraged to sign up for 2 events per week. They will sign up for events of their choosing to minimize feelings of anxiety or discomfort related to any conversation topic. To pre-empt negative experiences of participating in the intervention, especially in participants with MCI, we will provide training to use the OneClick platform, including detailed instructions about participation in the RCT and etiquette for participation, and quick-tip guides to make participation in the intervention enjoyable. We will provide printed materials for reference and contact information in case they require additional help.

## Section 10. INCLUSION/EXCLUSION

### 10A. List specific criteria for inclusion and exclusion of subjects in the study, including treatment and control groups.

Inclusion criteria: Study participants will be adults who are 65 years old and older. All participants will be living independently (i.e., not in assisted living or skilled nursing facilities), fluent in English, and will have adequate visual and auditory acuity to participate. They will have access to a computer or tablet and internet. They will have a Modified Telephone Interview for Cognitive Status (TICS-M) score of 22 or higher, Geriatric Depression Scale (GDS) score of 9 or below.

Additional inclusion criteria for the MCI group include memory complaints objective memory loss measured by a MoCA score of 20-25, and an absence of dementia (no evidence of significant impairment in social or occupational functioning as determined in the background questionnaire).

Exclusion criteria: Potential participants will be excluded if they have a TICS-M score lower than 22 or GDS score higher than 9. They will also be excluded if they have a MoCA score of 19 or less, or if they select "yes" to a diagnosis of Alzheimer's disease or other dementia in the Modified TechSage Background Questionnaire (TSBQ).

**10B. Explain how the inclusion/exclusion criteria will be assessed and by whom. If special expertise is required to evaluate screening responses or data, list who will make this evaluation and describe their training and experience.**

Inclusion/exclusion criteria will be determined by the research team using the screening forms. The research team has sufficient training and experience to carry out the proposed screening.

**10C. Drafts or final copies of all screening materials are attached.**  Yes  Not Applicable

**10D. Describe procedures to assure equitable selection of subjects. Justify the use of the groups marked in Section 9B. Selection criteria that target one sex, race, or ethnic group require a clear scientific rationale.**

Individuals of both genders will be included with no exclusions made based on racial or ethnic factors. All attempts will be made to recruit equal number of male and female participants. The study will include adults age 65 and older both with and without a diagnosis of MCI.

## Section 11. RECRUITMENT

**11A. Select all recruitment procedures that will be used.**

- Student subject pool, *please specify*:
- Email distribution
- MTurk, Qualtrics Panel, or similar online population, *please specify*:
- US Mail
- Flyers/brochures
- Website ad, online announcement (e.g. eWeek), or other online recruitment, *please specify*: Use of online announcement venues such as eWeek
- Newspaper ad
- Verbal announcement
- Other, *please specify*: Use of Clark-Lindsey Village in-house closed circuit TV system to display electronic flyers. Use of quarterly "President's Letter" including IRB-approved language from recruitment flyer.
- Not applicable (secondary data only)

**11B. Drafts or final copies of all recruitment materials (including verbal scripts) are attached.**

Yes  Not Applicable

**11C. For each group of participants, describe the details of the recruitment process.**

We will use our well-established multi-pronged recruitment strategies, which include word-of-mouth, email, and telephone scripts to members of established registries; flyers and brochures shared by community organizations and partners; advertisements in newspapers and newsletters; and personal visits to community events. All recruitment materials will be pre-approved by the IRB.

**At UIUC:** Participants with and without MCI will be recruited through the **I-HELP registry** and **[name] registry** of persons with MCI. The Human Factors and Aging Laboratory directed by [name] is part of a consortium that coordinates a registry of potential older research participants through the Beckman Institute at UIUC called I-HELP (Illinois Health and Engagement Lifespan Project). The I-HELP registry

currently contains 522 individuals including individuals with a diagnosis of MCI who are interested in participating in university research. [name] has a registry of individuals with MCI who are interested in participating in research studies. The MCI registry was developed by [name] research affiliation and ongoing MCI studies with the Carle Neuroscience Institute, which sees approximately 100 MCI patients per year. Additionally, interested participants will be recruited from Carle Neuroscience Institute in collaboration with [name], Staff Neurologist at Carle Hospital.

**At CJE:** CJE Senior Life supports about 20,000 older adults, which includes individuals with MCI, who live in independent living communities. Participants with and without MCI will be recruited from the 8 retirement community sites managed by CJE SeniorLife as well as their extensions. All sites are independent living. Sites in this study have been purposefully selected throughout the Chicagoland area to reflect a range of racial/ethnic backgrounds to maximize generalizability of findings. Recruitment flyers will be placed in resident mailboxes. Additionally, residents will receive a recruitment flyer during community town-hall meetings.

While general information about the study may be given in community settings, all formal recruitment will be completed via telephone to ensure privacy and individual service. The research team will complete encounter forms for all potential participants. The team will document all attempts to contact participants and will vary day and time of contact attempts if the participant is not reachable on the first attempt. During the recruitment pre-screening call, the research staff will follow a script to gather information about eligibility status and give information about the study. The research staff will clearly explain the time commitment, expectations for participation, and answer any questions the participant asks. If the person is eligible and expresses interest in enrolling, the team will schedule an appointment for obtaining informed consent and enrolling the participant in the study. If the person is ineligible, staff will follow a script to provide this information.

